1.2.3 Potential Risks

The following potential risks will be monitored during the study and are specified below:

Risks Related to Vaccination

In general, intramuscular (IM) injection may cause local itching, warmth, pain, tenderness, erythema, swelling, arm discomfort or bruising of the skin at vaccine injection sites.

Participants may exhibit general signs and symptoms associated with the administration of a vaccine, including fever, chills, rash, nausea/vomiting, general itching, headache, myalgia, arthralgia, and fatigue.

Young children may also experience loss of appetite, diarrhoea, decreased activity/lethargy, and irritability/crying. These side effects will be monitored, but are generally short-term and do not require treatment.

Participants may have an allergic reaction to the vaccine. An allergic reaction may cause a rash, hives or even anaphylaxis. Severe reactions are rare. Medications must be available in the clinic to treat serious allergic reactions.

Risks from Blood Draws

As with all clinical studies requiring blood sampling, there are risks associated with venipuncture and multiple blood sample collection. Blood drawing may cause pain, tenderness, bruising, bleeding, dizziness, vaso-vagal response, syncope, and, rarely, infection at the site where the blood is taken. The total blood volume to be collected is considered to be an acceptable amount of blood over this time period from the population in this study (see Section 15.1).

Concomitant Vaccination

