Parents/guardians will be instructed on how to record daily temperature using a thermometer provided for home use. The axillary temperature of the participant should be recorded in the diary in the evening of the day of vaccination, and then daily for the next 6 days at approximately the same time each day. The participant's temperature on Day 8 will be taken by study staff at the site clinic. If more than one measurement is made on any given day, the highest temperature of that day will be used in the CRF.

In this protocol, fever is defined as an endogenous elevation of body temperature $\geq 38^{\circ}\text{C}$, as recorded in at least one measurement.

Parents/guardians will also be instructed on how to note daily in the diary symptoms for 6 days post-vaccination (day of vaccination and the subsequent 6 days) any of the following events:

- body temperature
- fatigue/malaise
- chills
- headache
- nausea/vomiting
- muscle pain
- joint pain
- loss of appetite, in young children

Symptoms 7 days post vaccination (Day 8) will be assessed and recorded by study staff at the site clinic.

Physical Examination

A full physical examination will be performed at the screening visit. At subsequent study visits a brief, symptom-directed examination will be performed based on any clinically relevant issues, clinically relevant symptoms and medical history. The symptom-directed physical examination may be repeated if deemed necessary by the investigator. Physical examinations will be performed by the investigator or by a designated medically-trained clinician. Physical examination findings (i.e. abnormalities) prior to vaccination (Day 1) are to be recorded as medical history, but after vaccination as an AE.

Vital Signs

Axillary temperature, blood pressure, pulse/heart rate (beats per minute), and respiratory rate (breaths per minute) will be assessed.

Blood pressure and pulse/heart rate measurements will be assessed with a completely automated device. Manual techniques will be used only if an automated device is not available. Pulse/heart rate measurements should be preceded by at least 5 minutes of rest in a quiet setting without distractions.

Clinical Laboratory Tests

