11 ADVERSE EVENT REPORTING

Timely, accurate, and complete reporting and analysis of safety information from clinical studies are crucial for the protection of participants, investigators, and the sponsor, and are mandated by regulatory agencies worldwide. The sponsor has established standard operating procedures in conformity with regulatory requirements worldwide to ensure appropriate reporting of safety information; all clinical studies conducted by the sponsor or its affiliates are conducted in accordance with those procedures.

Method of Detecting AEs and Serious Adverse Events

Care will be taken not to introduce bias when detecting AEs or SAEs. Open-ended and nonleading verbal questioning of the participant's parent(s)/guardian is the preferred method to inquire about AE occurrence.

Solicited Adverse Events

Solicited AEs are predefined local (at the injection site) and systemic events for which the participant's parent/guardian is specifically questioned, and which are noted in the participant's diary.

Unsolicited Adverse Events

Unsolicited AEs are all AEs for which the participant's parent/guardian is not specifically questioned in the participant diary.

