11.3.1 All Adverse Events

Symptoms of solicited local and systemic AEs will be collected in the diary in the evening after the vaccination and then daily for the next 7 days. Unsolicited AEs will be reported from vaccination until 28 days post-vaccination.

Serious adverse events and/or special reporting situations that are related to study procedures will be reported from the time a signed and dated ICF is obtained onwards until the end of the study. All other SAEs and/or special reporting situations will be reported from the day of vaccination onwards until 28 days post-vaccination. The sponsor will evaluate any safety information that is spontaneously reported by an investigator beyond the time frame specified in the protocol.

The investigator will monitor and analyse the study data including all AE and clinical laboratory data as they become available and will make determinations regarding the severity of the adverse experiences and their relation to study intervention. All AEs will be deemed related to study intervention or not related to study intervention, according to Section 11.1.

The investigator or clinical designee must review both post-injection reactogenicity and other AE CRFs to insure the prompt and complete identification of all events that require expedited reporting as SAEs, invoke pausing rules, or are other serious and unexpected events.

All AEs, regardless of seriousness, severity, or presumed relationship to study intervention, must be recorded using medical terminology in the source document and the CRF. Whenever possible, diagnoses should be given when signs and symptoms are due to a common aetiology (e.g., cough, runny nose, sneezing, sore throat, and head congestion should be reported as "upper respiratory infection").

Investigators must record in the CRF their opinion concerning the relationship of the AE to study therapy. All measures required for AE management must be recorded in the source document and reported according to sponsor instructions.

The LSHTM assumes responsibility for appropriate reporting of AEs to the regulatory authorities. The LSHTM will also report to the vaccine manufacturer and investigator (and the head of the investigational institute, as required) all SUSARs. The investigator (or sponsor, as required) must report SUSARs to the appropriate IEC that approved the protocol unless otherwise required and documented by the IEC.

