Irritability	Easily consolable; minimal or no interference with activity. Episodes of continuous crying <60 min.	Difficult to console. Episodes of continuous crying >60 min <120 min	Inconsolable, prevents daily activity. Episodes of continuous crying >120 min	Hospitalization or ER visit for treatment
Decreased Activity	Minimal decrease in alertness, minimal or no interference with activity	Some interference with activity, slightly subdued	unable to achieve normal level of alertness, lethargic	ER visit or hospitalization for treatment or life-threatening consequences
Neuropathy/ Lower Motor Neuropathy	----	Mild transient Paresthesia only	Persistent or progressive paresthesia, burning sensation in feet, or mild dysesthesia; no weakness; mild to moderate deep tendon reflex changes; no sensory loss	Onset of significant weakness, decrease or loss of DTRs, sensory loss in "stocking glove" distribution, radicular sensory loss, multiple cranial nerve involvement; bladder or bowel dysfunction, fasciculations, respiratory embarrassment from chest wall weakness.
Myopathy or Neuromuscular Junction Impairment	Normal or mild (<2 x ULN) CPK elevation	Mild proximal weakness and/or atrophy not affecting gross motor function. Mild myalgias, +/- mild CPK elevation (<2 x ULN)	Proximal muscle weakness and/or atrophy affecting motor function +/- CPK elevation; or severe myalgias with CPK >2 x ULN;	Onset of myasthenia-like symptoms (fatigable weakness with external, variable ophthalmoplegia and/or ptosis), or neuromuscular junction blockade (acute paralysis) symptoms
OTHER				
	Grade 1	Grade 2	Grade 3	Grade 4
Fever/pyrexia	38.0 - 38.4 °C or 100.4 - 101.1 °F	38.5 - 38.9 °C or 101.2 - 102.0 °F	39.0 - 40.0 °C or 102.1 - 104.0 °F	Greater than 40 °C or 104.0 °F
Acute allergic reaction	Pruritus without Rash	Pruritic Rash	Mild Urticaria	Severe Urticaria Anaphylaxis, Angioedema
Stomatitis	Mild discomfort	Painful, difficulty swallowing, but able to eat and drink	Painful: unable to swallow solids	Painful: unable to swallow liquids; requires IV fluids
Illness or clinical adverse event (as defined according to applicable regulations)	No interference with activity	Some interference with activity not requiring medical intervention	Prevents daily activity and requires medical intervention	Hospitalization

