6.1.3. Analysis

AEs (solicited and unsolicited) will be tabulated by presenting the number and percentage of participants having at least one of the observed AEs.

The unsolicited AEs will be summarised by System Organ Classification (SOC) and Preferred Term (PT). The solicited AEs will be summarized by class (local, systemic) and PT. For solicited as well as unsolicited AEs, tables focussing on severity and relatedness to vaccine will be created.

SAEs, AEs with fatal outcomes, AEs leading to permanent discontinuation of vaccine, Grade 3 AEs and AESIs will be listed. Tables, summarizing all those parameters will also be created.

For the solicited local and systemic AEs, the duration and time to onset of the events will also be summarized. If a participant experience more than one occurrence of a solicited event, the maximum duration of the events will be used. The time to first onset is defined as:

[date of first onset – reference date+1]

The reference date is the start date of each vaccination period. Duration and time to onset of AEs will be expressed in days.

Summaries, listings, datasets, and/or participant narratives may be provided as appropriate, for those participants who die, or experience a SAE.

The analysis of AEs will be based on MeDRA coded terms as provided in the clinical database.

A listing of all SAEs during the study period will be provided. A listing of all AESIs (if flagged in the database) will be presented as well.

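### Loss of appetite is solicited only in an undefined set of young children and is missing from the SAP's solicited list, so its rate has no settled denominator and no sure place in the tables

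*Protocol*

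**What the plan says.** **Collection.** Protocol 1.2.3 (Potential Risks) names four reactions particular to young children: "Young children may also experience loss of appetite, diarrhoea, decreased activity/lethargy, and irritability/crying. These side effects will be monitored". The solicited systemic items in Protocol 8.3.1 include one of the four by name, restricted as "loss of appetite, in young children". The list also contains "fatigue/malaise" and chills, without an age restriction. Events outside the diary have their own route in Protocol 11: "Unsolicited AEs are all AEs for which the participant's parent/guardian is not specifically questioned in the participant diary". Their collection window is in 11.3.1: "Unsolicited AEs will be reported from vaccination until 28 days post-vaccination".

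**Analysis.** SAP 2.3.1 puts all safety analysis on the full analysis set, and SAP 2.4 shows it by age group, 1-3 and 4-11 years. The protocol synopsis makes clear that this is age at dose 1 in the parent trial. SAP 6.1.3 says that AEs "will be tabulated by presenting the number and percentage of participants having at least one of the observed AEs". SAP Attachment 3 analyses a day with no diary entry as a day with no event.

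**Term lists.** SAP 6.1 says the analysis uses the diary-card terms, and SAP 3 reports no change from the protocol's planned analysis. The solicited systemic list in SAP 6.1.1.2 nevertheless contains neither loss of appetite nor chills.

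**The concern.** Tolerability of the booster is a primary objective and is reported by age group, with about 25 children in each. By the protocol's own background (1.1), decreased appetite was the commonest solicited systemic AE in the 1-3 years cohort of the earlier paediatric trials. It is therefore a reaction that readers will look for in the younger group.

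Two things about it are left open. First, nobody reading the protocol can tell which children are to be asked. The reporting groups are fixed by age at dose 1, more than two years earlier, so an age rule applied at the booster visit need not line up with them. If it does not, children who were never asked sit in the denominator as if they had answered no. Second, a programmer following SAP 6.1.1.2 literally would not produce a solicited table row for loss of appetite or chills at all, although both are collected.

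**Working it through.** **1. Plan figures.** There is no powered figure to reproduce. The sample is a convenience sample of about 25 + 25 = 50, and safety is descriptive.

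**2. Protocol list against SAP list.** Protocol 8.3.1 has eight systemic items. Six have a counterpart in SAP 6.1.1.2: temperature (as fever), fatigue, headache, nausea/vomiting, muscle pain and joint pain. The other 8 − 6 = 2, chills and loss of appetite, have none. This conflicts with SAP 6.1 (diary-card terms) and sits badly with SAP 3 (no changes).

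**3. Can an age rule split a reporting group?** The synopsis puts the primary regimen more than 2 years before the booster. Lower bounds on age at booster are therefore:

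- aged 1 at dose 1: over 1 + 2 = 3 years
- aged 3 at dose 1: over 3 + 2 = 5 years
- aged 4 at dose 1: over 4 + 2 = 6 years

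The documents use several age cuts for other purposes: under 5 (haemoglobin limit, inclusion criterion 6), under 6 (blood volumes, Time and Events Schedule) and 1-3 years at dose 1 (recruitment). None is tied to the diary item.

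- An under-5 rule leaves out every child aged 3 at dose 1 but can include a child aged 1.
- An under-6 rule can fall either side of a child aged 3 at dose 1, and leaves out the whole 4-11 years group.
- A rule based on 1-3 years at dose 1 splits nothing.

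The upper end of the interval is not given, so where a split would fall cannot be worked out.

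**4. Are unasked children counted as event-free?** The full analysis set is everyone vaccinated (SAP 2.3.1), the percentage is of participants (SAP 6.1.3), and an empty diary day means no event (SAP Attachment 3). Together these make an unasked child a child without the event. Laboratory data, by contrast, get a non-missing denominator (SAP 6.2.1); no such rule is given for solicited AEs.

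**5. Size of the dilution.** Let m be the number asked in a group of 25 and x the number with the event. The rate among those asked is x/m, the tabulated rate is x/25, and their ratio is m/25. The value of m is an assumption throughout.

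| m asked of 25 | tabulated rate ÷ rate among asked |
|---|---|
| 25 | 1.0 |
| 20 | 0.8 |
| 15 | 0.6 |
| 10 | 0.4 |
| 5 | 0.2 |

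Examples with Clopper-Pearson 95% intervals, the SAP's method:

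- **Whole group asked:** 5/25 = 20% (6.8 to 40.7%). No error.
- **Group split, m = 10:** 3/10 = 30% (6.7 to 65.2%) is tabulated as 3/25 = 12% (2.5 to 31.2%).
- **Groups pooled, only one asked:** 5/25 = 20% (6.8 to 40.7%) becomes 5/50 = 10% (3.3 to 21.8%).
- **4-11 years group not asked at all:** 0/25 = 0% (0 to 13.7%), which would look like an observed absence.

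**The case against.** **The denominator may be right.** If young children means the 1-3 years at dose 1 group, that group's rate is correct, and safety is planned by group rather than pooled. SAP 6.1.3 does not itself name a denominator. The diary form is not among the documents and may print an age rule, and the study runs in one place, Kambia, so there is no variation between sites. All of this stands. A reader might infer that the rate simply has the wrong denominator; the documents do not support that. They leave it undefined, and it is wrong only under some readings.

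**Section 1.2.3 is not broken.** A reader might also infer that three of the four young-child reactions go unmonitored, or that reactogenicity in the younger group is under-counted. Monitored does not mean solicited. Several reactions that 1.2.3 lists for all participants, such as rash and bruising, are not diary items either. Events outside the diary are collected as unsolicited AEs for 28 days, and parents are questioned: "Open-ended and nonleading verbal questioning of the participant's parent(s)/guardian is the preferred method to inquire about AE occurrence". Lethargy overlaps "fatigue/malaise". Prompted items may well be captured more completely than unprompted ones, but the documents give no capture rate, so an under-count is neither shown nor measurable.

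**Appendix 1 does not show that these belong in the diary.** It grades irritability (Grade 1 begins "Easily consolable; minimal or no interference with activity"), diarrhoea and decreased activity. But Protocol 11.1.3 applies that table to AEs other than solicited ones, which fits unsolicited collection.

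**What the objections leave untouched.** The age restriction is undefined, no denominator is stated for an item asked of only some children, and SAP 6.1.1.2 does not match Protocol 8.3.1.

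**Conclusion.** The point holds in this limited form. Loss of appetite is solicited in an undefined subset of children. Under the SAP's rules its rate is diluted by the factor m/25 in any reported group of which only m of 25 are asked, and likewise when an asked group is pooled with an unasked one. The error is nil if the whole 1-3 years group is asked and only that group's rate is shown. It is a factor of 0.4 if 10 of 25 are asked. Because m is not stated, neither the presence nor the size of an error can be established; the worked rates are illustrations. They also rest on reading the missing-day rule as covering children who were never asked, which is the natural reading but is not spelled out.

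The mismatch between the SAP's solicited systemic list and the protocol's is not conditional: two collected items, one of them the commonest systemic reaction in the earlier 1-3 years cohort, have no listed place in the solicited analysis. Nothing here touches sample size or hypotheses. It is a low-cost correction to a descriptive primary safety result.

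**What to change.** 1. **Protocol 8.3.1 and the diary:** ask about loss of appetite for every participant. This removes the need for an age definition and makes the full-analysis-set denominator correct in both groups and overall.
2. **SAP 6.1.1.2:** add loss of appetite and chills, so that the list matches Protocol 8.3.1 and the diary-card rule in SAP 6.1. The diary change alone is not enough, because the item might still not be tabulated as solicited.
3. **If the item stays restricted:** define young children by age at booster in Protocol 8.3.1, record who was asked, and state in SAP 6.1.3 that the denominator is the children asked.

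**Cost.** One more diary line for the older children, and some background appetite loss recorded in them with no control group to set it against. Changing the protocol and diary needs an amendment and ethics committee approval (Protocol 15.2.2 and 16.1). The SAP edit adds two table rows.

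**Optional.** Adding diarrhoea and irritability/crying to the diary would give prompted collection, but it is a design preference and does not correct an error. It would also need squaring with Protocol 11.1.3, which excludes solicited AEs from the Appendix 1 grading.

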1.2.3 Overall Benefit/Risk Assessment

Based on the available data and proposed safety measures, the overall benefit/risk assessment for this clinical study is considered acceptable for the following reasons:

- To date, safety data from the studies in the clinical development program revealed no significant safety issues (see Section 1.1). Further experience from Ad26.ZEBOV Filo will be gained from currently ongoing clinical studies.
- For all participants, there are pre-specified pausing rules that would result in pausing of further vaccination if predefined conditions occur, preventing exposure of new participants to study intervention until an independent medical reviewer evaluates all safety data (see Sections 3.1, 8.3, 10.7).
- Only participants who meet all inclusion criteria and none of the exclusion criteria (specified in Section 4) will be allowed to participate in this study. The selection criteria include adequate provisions to minimize the risk and protect the well-being of participants in the study.
- Several safety measures are included in this protocol to minimize the potential risk to participants, including the following:
 - Participants will remain at the site for at least 30 minutes after each vaccination to monitor the development of any acute reactions, or longer if deemed necessary by the investigator (e.g. in case of grade 3 AEs). Refer to Section 6 for more information on emergency care.
 - Safety evaluations (physical examinations and vital sign measurements) will be performed at scheduled visits during the study, as indicated in the TIME AND EVENTS SCHEDULE.
 - The investigator or clinical designee will document unsolicited AEs from the vaccination (Day 1) onwards until 28 days post-vaccination (Day 29). The investigator or clinical designee will document serious AEs and/or special reporting situations that are related to study procedures from the time a signed and dated informed consent form (ICF) is obtained onwards until the end of the study.
 - Any clinically significant abnormalities (including those persisting at the end of the study/early withdrawal) will be followed by the investigator until resolution or until a clinically stable endpoint is reached.
 - If acute illness (excluding minor illnesses such as diarrhoea or mild upper respiratory tract infection) or axillary temperature $\geq 38^{\circ}\text{C}$ is present at the scheduled time for vaccination, the participant may be rescheduled for vaccination at a later time point within the window allowed for screening, or be withdrawn from vaccination at the discretion of the investigator and after consultation with the sponsor (see Section 6.1).

1.3 OVERALL RATIONALE FOR THE STUDY

Over 600 paediatric participants have received the Ad26.ZEBOV, MVA-BN-Filo Ebola vaccine regimen in the EBL2002 and EBL3001 clinical trials. [4, 5] The vaccine regimen was well-tolerated and highly immunogenic in children, however, the durability of the immune response is not known. In adults previously vaccinated with the Ad26.ZEBOV and MVA-BN-Filo regimen, an Ad26.ZEBOV booster vaccination was safe and induced a strong anamnestic response. [6] It is important to establish the safety and immunogenicity of a booster dose of Ad26.ZEBOV in children, as this can guide the clinical use of the vaccine regimen in this group. For example, it could support the strategy of boosting immunised children at the start of an Ebola outbreak.

